# 3.2 SCHEDULE OF EVENTS: TREATMENT ARM

Study Period & Events	Screening	Randomize	Treatment Arm Treatment & Response Assessment						Progression	Follow up 	End of Study		
Timing: Study Visits (+/- 7 days) or Events	D -14 to 0 	D 0	W 2	W 4	w 8	W 12	W 16	W 20	W 24	W Q8		W Q8	
Informed Consent	x			Г									
Demographics	x												
Medical History	x												
Physical Exam (PE)	x												
Categorization of PVT	x				x		X		X	X			
ECOG Performance Status	x		X	X	X	X	X	X	X	X		X	
Child Pugh Status	x				X		X		X	х		X	
Medication & Prior Treatment History	x												
Hematology	x			X	X	X	X	X	X				
Coagulation	x			X	x	х	х	х	х				
Chemistry panel, liver function tests	x		X	X	x	х	х	х	х				
Serum Pregnancy 	x												
Tumor marker (AFP)	x				X		X		X	X			
Bone Scintigraphy  (if AFP >400ng/mL)	x						X					(Q6 mo)	
Liver Volume/Tumor mass	x												
Review Eligibility Criteria	x												
Randomize Patient		X											
FACT-Hep questionnaire 	x			x	x	x	X	X	X	x		X	
Hepatic Angiogram  , TcMAA scan  , TS Dose Calculation			x										
Order TS			X										
Administer TS treatment 				X									
Spiral CT of abdomen/pelvis	x 				x		х		х	x			
Spiral CT of chest 	Χ 						х			X			
Assess/Report Adverse Events	x		X	x	x	х	х	х	х	X		X	X
Review/Record Study Treatment			X	x								X	
Record Concurrent Medication	x		X	x	x	x	x	x	x	x		X 	X
Optional TheraSphere Retreatment 												x	
Final Endpoint Efficacy/Safety documentation & exit patient													x

<sup>1 Visits can be conducted by telephone at the investigator's discretion, if a PS ≥ 2 (symptomatic progression) is assessed and whenever in the best interest of the patient

 Results from tests and examinations done as part of clinical patient management within 14 days of randomization may be used to satisfy screening requirements to avoid unnecessary duplicative patient testing

 Female patients of childbearing potential only—can be repeated at physician discretion before repeat TheraSphere treatments

 Required for patients with AFP >400 ng/mL to assess metastatic disease at screening, Week 16 then every 6 months

<sup>5 Subjects to complete questionnaire at each study visit; completion not required for telephone follow-up visits

<sup>6 Pre-treatment evaluation is always done before the first TheraSphere treatment and prior to subsequent treatments as needed

<sup>7 TheraSphere must be administered within 4 weeks of randomization

<sup>8 Images taken up to 28 days in advance of randomization can be used for baseline images

 Imaging to be scheduled every 16 weeks from randomization at alternate Q8 week follow up visits

<sup>10 Document liver treatment medications only; medications used for supportive care do not require documentation

 A maximum of 2 re-treatments with TheraSphere are allowed following hepatic progression for lesions amenable to TheraSphere treatment

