# Treatment Arm Study Treatment (TheraSphere)

Within 2 weeks from randomization, hepatic angiography will be performed to assess hepatic vascular anatomy and tumor hypervascularity, followed by a 99mTc-MAA scan to rule-out gastrointestinal flow or unacceptable lung shunting. Embolization may be performed, if necessary, to close off gastrointestinal flow or to perform tumor redistribution so that the patient can meet eligibility criteria.

Patients will not be eligible for TheraSphere infusion if the potential radiation dose to the lungs exceeds 30 Gy for a single treatment or cumulative 50 Gy or embolization cannot be performed to effectively block GI blood flow from the hepatic arterial system. If radiation exposure to the lungs exceeds 30 Gy, dose reduction of TheraSphere is permitted (minimum dose allowed is 80 Gy ± 10%). These patients will be eligible to receive sorafenib SOC therapy and will be included in the Treatment Arm Intent-to-Treat analysis, but not in the Treatment Arm Per-Protocol analysis.

TheraSphere Treatment: TheraSphere treatment should occur within 28 days of randomization. The number of infusions required to achieve lobar treatment will be determined by the Investigator, based on the hepatic vascular anatomy.

Patients will receive TheraSphere, at a dose consistent with the approved product label, to the treated lobe of the liver. A target dose of 120 Gy ± 10% is advised. Thera Sphere Re-treatment: Re-treatment of the same patient/lobe with further cycles of TheraSphere is permitted if a treatable progression is detected during follow-up evaluations. Any retreatment should take place at least 28 days from the last TheraSphere treatment administered to that lobe. Patients can receive a subsequent TheraSphere administration in the absence of radiological progression criteria at investigator discretion. Patients must meet initial eligibility criteria to receive subsequent treatments. A maximum of three (3) TheraSphere administrations are permitted in total.

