- 17. No previous treatment with Sorafenib for more than 4 weeks during the 2 previous months; no prior sorafenib-related toxicity at any dose and/or duration defined as documented sorafenib-related grade 3 or 4 adverse events that led to sorafenib discontinuation
- 18. No initiation of any other anti-tumor therapy including chemotherapy, radioembolization (maximum lung shunt of 20% for prior radioembolization) or investigational drug treatment within 30 days before the beginning of the study
- 19. In case of patients progressing from an intermediate to an advance stage because of occurrence of PVT, enrolment is allowed if previous conventional or drug eluting TACE was performed at least 3 months prior to screening phase
- 20. Patients cannot be on a liver transplantation list
- 21. No history of organ allograft
- 22. No contraindication to angiography or selective visceral catheterization
- No history of severe allergy or intolerance to contrast agents, narcotics, sedatives or atropine that cannot be managed medically
- 24. No previous external beam radiation treatment to the liver
- 25. No evidence of continuing adverse effect of prior therapy
- No active GI bleeding and any bleeding diathesis or coagulopathy that is not correctable by usual therapy or hemostatic agents (e.g., closure device)
- No evidence of any disease or condition that would place the patient at undue risk and preclude safe use of microspheres (TheraSphere®) treatment
- Negative serum pregnancy test in females of child-bearing potential; patients who are breast-feeding cannot participate in this trial
- Life expectancy of greater than 3 months
- 30. No participation in concurrent interventional clinical trials
- Signed informed consent

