#### 9.1.3 Patients randomized to the Treatment Arm

#### 9.1.3.1 WEEKS 1-4 FOLLOWING RANDOMIZATION

The following study-related activities will be completed:

- 1. Complete appropriate clinical laboratory tests, including AFP, as described in Section 9.2.10 within 7 days prior to TheraSphere administration.
- 2. Conduct pre-TheraSphere evaluation within Week 2, as described in Section 9.2.16.1.2, and administer TheraSphere by the end of Week 4 to patients able to receive TheraSphere treatment as described in Section 9.2.16.1.7. For patients who are determined to be not treatable with

TheraSphere following the pretreatment evaluation, patients may begin sorafenib therapy as soon as possible.

- 3. Record details on the clinical assessments and administration of TheraSphere.
- Record any treatment and concurrent medications and any adverse events as described in Sections 9.2.18, 9.2.19 and 12.3.

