#### 9.1.3.2 THERASPHERE RE-TREATMENT

Patients can receive a subsequent TheraSphere administration in the absence of radiological progression criteria at investigator discretion Patients must meet initial eligibility criteria to receive subsequent treatments. A maximum of three (3) TheraSphere administrations are permitted in total. TheraSphere treatments may be administered after hepatic progression if the lesions are amenable to treatment. Any retreatment should take place at least 28 days from the last TheraSphere treatment. These optional treatments are not required protocol treatments and are administered at the discretion of the investigator. The following activities will take place:

- Complete appropriate clinical laboratory tests, as described in Section 9.2.10.
- Conduct pre-TheraSphere evaluation as with interventions as indicated and administer TheraSphere as described in Sections 9.2.16.1.2 and 9.2.16.1.7.
- 3. Record details on the clinical assessments and administration of TheraSphere.
- Record any treatment and concurrent medications and any adverse events as described in Sections 9.2.18, 9.2.19 and 12.3.
- Record Child Pugh status as described in Section 9.2.7

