#### 9.2.16.1.1 RE-TREATMENT

Patients can receive a subsequent TheraSphere administration in the absence of radiological progression criteria at investigator discretion. During follow-up, for patients in the Treatment arm who have demonstrated hepatic progression with hepatic lesions amenable to TheraSphere., re-treatment with TheraSphere is allowed. Any re-treatment should take place at least 28 days from the last TheraSphere treatment.

Patients must meet initial eligibility criteria for TheraSphere treatment (Section 8.1) to receive subsequent treatments. A maximum of three (3) TheraSphere administrations are permitted in total.

Patients will undergo additional pre-treatment evaluations as described in Section 9.2.16.1.2 at the investigator's discretion prior to administration of subsequent TheraSphere treatments to assess and address any changes in extra-hepatic shunting that may have developed.

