#### 9.2.16.1.8 THERASPHERE ADMINISTRATION DOCUMENTATION

Any technical problems or complications related to the delivery of TheraSphere treatment to the patient must be documented in the medical record. The details of any event and its impact on the patient should be documented on an Adverse Event eCRF. Patients in the Treatment arm must certify continued eligibility prior to administration of TheraSphere. A new blood draw for labs and pregnancy and an ECOG Performance Status test may be performed within 7 days before TheraSphere administration at physician discretion to confirm baseline results.

Using institutional practices, the activity of each vial of TheraSphere will be determined prior to administration. This activity will be used to calculate the actual dose delivered to the liver and lung which will be recorded on the appropriate eCRF.

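### After screening, no serum pregnancy test is required before any TheraSphere administration, first or repeat; each later test is left to physician discretion

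*Protocol*

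**What the plan says.** The serum pregnancy row in the treatment-arm schedule (protocol Section 3.2) has one mark, at screening, and Section 9.2.11 likewise places the test at the screening visit. Two later statements concern further testing, and both are permissive:

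- Section 3.2, footnote 3: the test "can be repeated at physician discretion before repeat TheraSphere treatments".
- Section 9.2.16.1.8, on TheraSphere administration generally: a new blood draw for laboratory tests and "pregnancy and an ECOG Performance Status test may be performed within 7 days before TheraSphere administration at physician discretion to confirm baseline results".

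Other provisions are mandatory:

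- Section 9.2.16.1.8, immediately before the optional draw: "Patients in the Treatment arm must certify continued eligibility prior to administration of TheraSphere".
- Section 9.2.16.1.1: "Patients must meet initial eligibility criteria for TheraSphere treatment (Section 8.1) to receive subsequent treatments".
- Section 8.1 lists among those criteria: "Negative serum pregnancy test in females of child-bearing potential".
- Section 9.1.3.1, before the first administration: "Complete appropriate clinical laboratory tests, including AFP, as described in Section 9.2.10 within 7 days prior to TheraSphere administration".
- Section 9.1.3.2, before a repeat: "Complete appropriate clinical laboratory tests, as described in Section 9.2.10".

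The list in Section 9.2.10 covers hematology, coagulation, chemistry and AFP. It has no pregnancy test. SAP Section 6.1, Table 2, repeats the schedule footnote and adds nothing.

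**The concern.** The investigator must certify that the patient is still eligible, but the one assay that would verify the pregnancy criterion is optional. A site that follows the protocol to the letter can certify eligibility on a screening result that is weeks or months old, while another site may read the re-treatment condition as calling for a new test. At stake is possible fetal exposure to a radioactive device, which would be serious and irreversible. Power, type I error and the efficacy analyses are not involved.

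**Working it through.** There is no planned figure to reproduce. The check has two parts: whether any provision makes a later test compulsory, and how old the screening result can be.

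**1. Is a later test required anywhere?**

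| Time point | Required laboratory tests | Pregnancy test |
|---|---|---|
| Screening | Section 9.2.10 list | Required (3.2, 9.2.11) |
| Before first administration | Section 9.2.10 list, within 7 days (9.1.3.1) | Optional (9.2.16.1.8) |
| Before a repeat | Section 9.2.10 list, no window stated (9.1.3.2) | Optional (3.2 footnote 3; 9.2.16.1.8) |

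No other provision in the two documents requires the test after screening.

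**2. Age of the only required test.**

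Inputs:

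- Screening falls on day -14 to day 0 (Sections 3.2 and 9.1.1).
- In the synopsis, "TheraSphere treatment should occur within 28 days of randomization"; so the first administration is on day d, with d at most 28.
- Re-treatment comes at least 28 days after the last treatment (Sections 9.1.3.2 and 9.2.16.1.1). No upper limit is given.
- At most three administrations in total.

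Formulas:

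- Age at first administration: d to d + 14.
- Age at first re-treatment: at least d + 28 to d + 42.
- Age at second re-treatment: at least d + 56 to d + 70.

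| First administration | At first (days) | At first re-treatment (days) | At second re-treatment (days) |
|---|---|---|---|
| d = 28 (latest planned) | 28 to 42 | at least 56 to 70 | at least 84 to 98 |
| d = 14 (assumed example) | 14 to 28 | at least 42 to 56 | at least 70 to 84 |

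The week 8 scan on day 56 fits the first row: a repeat on that day is exactly 28 days after a day 28 administration, and the test is then 56 to 70 days old.

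Two limits apply. The 28-day floors hold for re-treatments only. The trial schema (Section 2) allows the initial treatment to be planned in one or two sessions, and a second planned session may come sooner than 28 days after the first. The synopsis also ties the 28-day gap to the same lobe, whereas Sections 9.1.3.2 and 9.2.16.1.1 do not; the table follows those two sections.

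With a test required within 7 days before each session, every age in the table becomes at most 7 days.

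**The case against.** The strongest reply is that the protocol already fixes the status and leaves only its verification to the physician, which is a coherent choice. Continued eligibility must be certified, and Section 9.2.11 requires contraception and advice against pregnancy throughout enrolment. The synopsis has TheraSphere given according to the approved label, and Section 13.10 binds investigators to radiation-safety policy. If either source requires a test, that test is in effect a protocol obligation.

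Part of this stands. The label appears only as links and local policies are not given, so the gap can be stated only for the text in hand. But contraception and certification do not supply a current result, and Section 9.2.22 itself foresees removal for pregnancy. Deferring to local policy also allows practice to differ across up to 25 sites.

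A reader might infer a flat contradiction: Section 8.1 demands a negative test for re-treatment and footnote 3 waives it. The documents do not carry that far. Section 9.2.16.1.1 speaks of eligibility for TheraSphere treatment, which may mean suitability for the device. Nor can Section 8.1 be reapplied literally in full, because it requires unilobar disease while Section 9.2.16.3 allows re-treatment of contralateral progression. The missing test does not depend on how that wording is read.

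A reader might also take the cap of three to apply to infusions. It applies to administrations or sessions. The synopsis leaves the number of infusions needed for lobar treatment to the investigator, and Section 9.2.16.1.3 contemplates three or more.

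Finally, SAP Section 5 records that the study was terminated early. That limits the practical benefit to any remaining treatments and to reuse of this protocol text.

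**Conclusion.** The point holds as a safety improvement. On the documents alone, screening is the only time a pregnancy test is required, and up to three administrations may rest on it. The result can be up to 42 days old at a first administration on day 28 and is at least 28 days older at each re-treatment. An earlier first administration shortens these ages; a longer interval to re-treatment lengthens them without a stated limit.

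This assumes that neither the label nor local policy already requires a test. The number of women of childbearing potential is not given and is probably small, so no expected number of exposures can be computed. The documents do not show that a pregnant woman would be treated, only that the protocol text does not require the check that would detect it.

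**What to change.** Adopt one rule: women of childbearing potential must have a negative serum pregnancy test within 7 days before each TheraSphere administration session, first and repeat. The 7-day window already appears in Sections 9.1.3.1 and 9.2.16.1.8.

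- Section 3.2: add marks to the serum pregnancy row and replace the discretionary wording of footnote 3.
- Sections 9.1.3.1 and 9.1.3.2: add the test to the required activities before first and repeat administration.
- Section 9.2.11: state the rule alongside the screening test.
- Section 9.2.16.1.8: make the pregnancy test mandatory.
- Log a missed or late test under Section 14, category 7, which covers tests done out of window or not done.
- SAP Section 6.1, Table 2, footnote 3 may be aligned for consistency.

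The cost is at most three extra assays per affected woman. Before the first administration, the assay can use the blood drawn under Section 9.1.3.1. Before repeats, a re-timed or additional draw may be needed, because Section 9.1.3.2 sets no 7-day window. No analysis changes.

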#### LIST OF ABBREVIATIONS

- AE Adverse Event
- AFP Alphafetoprotein
- ALT Alanine Transaminase
- AST Aspartate Transaminase
- BUN Blood Urea Nitrogen
- CBC Complete Blood Count
- COPD Chronic Obstructive Pulmonary Disease
- CP- Child-Pugh
- CRC Colorectal Cancer
- Cr Chromium
- CR Complete Response
- CT Computed Tomography
- CTCAE Common Toxicity Criteria for Adverse Events
- EASL- European Association for the Study of the Liver
- ECOG Eastern Cooperative Oncology Group
- eCRF electronic Case Report Form
- FACT-Hep Functional Assessment of Cancer Therapy Hepatobiliary Questionnaire
- FHSI8 Functional Assessment of Cancer Therapy Hepatobiliary Symptom Index 8
- GBq gigabecquerel
- GI gastrointestinal
- Gy Gray, a measure of irradiation dose
- **HBV- Hepatitis B Virus**
- HCC Hepatocellular Carcinoma
- HCV Hepatitis C Virus
- HDE Humanitarian Device Exemption
- ICF Informed Consent Form
- INR International Normalized Ratio for prothrombin time
- IRB Institutional Review Board
- ITT Intent–to-Treat
- LFT Liver Function Tests
- mRECIST- modified RECIST
- MRI Magnetic Resonance Imaging
- NCI National Cancer Institute
- PD Progressive Disease

PE - Physical Exam

PFS - Progression Free Survival

PLT – Platelet Count

PPP – Per Protocol Population

PR – Partial Response

PRO – Patient Reported Outcome

PS - Performance Status

PT - Prothrombin Time

PTT - Partial Thromboplastin Time

**PVT- Portal Vein Thrombosis** 

PVTT - Portal Vein Tumor Thrombosis

RECIST – Response Evaluation Criteria in Solid Tumor

SAE – Serious Adverse Event

SD – Stable Disease

SOC - Standard of Care

99mTC-MAA – Technetium-99m Magroaggregated Albumin

TEAE – Treatment emergent adverse events

TS – TheraSphere

TTDQoL - Time to deterioration in QoL

TTP - Time-to-Progression

TTSP - Time to symptomatic progression

UADE – Unanticipated Adverse Device Effect

US - Ultrasound

WBC - White Blood Cells

Y-90 (Y-88, Y-91) - Ytrium-90 and isotopes

Y90-TARE- 90Yttrium trans-arterial radioembolization

## 5 BACKGROUND AND RATIONALE

#### **5.1** GENERAL DEVICE DESCRIPTION

TheraSphere® consists of insoluble glass microspheres in which yttrium-90 is an integral component of the glass. The sphere diameter ranges from 20 to 30 µm with 22,000 to 73,000 microspheres per milligram. TheraSphere is available in dose sizes ranging from 3 GBq to 20 GBq, each supplied in 0.6 mL of sterile, pyrogen-free water contained in a 1.0 mL vial secured within a clear acrylic vial shield. A pre-assembled single-use TheraSphere Administration Set is provided for each dose. Each user site is provided with a re-useable TheraSphere Administration Accessory Kit that provides both radiation protection for the user and physical support of the dose vial and Administration Set during administration of the product.

Yttrium-90 is a pure beta emitter which decays to stable zirconium-90 with a physical half-life of 64.1 hours. The average energy of the beta emissions from yttrium-90 is 0.9367 MeV with mean tissue penetration of approximately 2.5 mm.

TheraSphere is administered through the hepatic artery which supplies blood to tumor tissue (the portal vein supplies blood to the normal hepatic tissue). The microspheres are trapped in the vasculature of the tumor due to arteriolar capillary blockage where they exert a local radiotherapeutic effect. In clinical use, the glass microspheres remain permanently trapped in the vasculature where the isotope decays to infinity leaving background radiation with no therapeutic value.

#### 5.2 GLOBAL REGULATORY STATUS OF THERASPHERE

TheraSphere received a Humanitarian Device Exemption (HDE) from the United States Food and Drug Administration (FDA) in 1999 (HDE H980006) and is currently approved for use in radiation treatment or as a neoadjuvant to surgery or transplantation in patients with unresectable hepatocellular carcinoma (HCC) who can have placement of appropriately positioned hepatic arterial catheters. The device is also indicated for HCC patients with partial or branch portal vein thrombosis/occlusion, when clinical evaluation warrants the treatment. The US package insert is provided in Appendix 1(a).

TheraSphere is approved for use in Europe for the treatment of hepatic neoplasia. TheraSphere is approved in Canada for the treatment of hepatic neoplasia in patients who have appropriately positioned arterial catheters. In addition, TheraSphere is available in Russia, India, South Africa, Turkey and Kuwait for the treatment of hepatic neoplasia. The current package insert for Canada is provided in Appendix 1 (b); current Instructions for Use document for Europe is provided in Appendix 1(c).

#### 5.3 RATIONALE FOR THE TREATMENT OF HEPATOCELLULAR CARCINOMA

According to the American Cancer Society, primary liver cancer is a major health problem worldwide. Globally, it is the fifth most commonly diagnosed cancer in men and eighth most common in women, with more than 700,000 new cases in 2007. It is the third leading cause of cancer death in men and sixth among women. Hepatocellular carcinoma is associated with known risk factors including chronic viral hepatitis (types B and C), alcohol intake and aflatoxin exposure, the presence of which vary geographically. In North America and Europe, chronic hepatitis C is a major risk factor while chronic hepatitis B is a major risk factor worldwide.

In 2007, the FDA and EMEA approved sorafenib tosylate (Nexavar - a registered trademark of Onyx Pharmaceuticals, Inc. and Bayer HealthCare Pharmaceuticals, Inc.), a small molecule Raf kinase and VEGF receptor kinase inhibitor, for the treatment of patients with unresectable hepatocellular carcinoma (HCC).

The approval was based on the results of an international, multicenter, randomized, double-blind, placebocontrolled trial (SHARP5 trial) in patients with unresectable, biopsy-proven hepatocellular carcinoma. Overall survival was the primary efficacy endpoint. A total of 602 patients recruited primarily from Europe and North America were randomized; 299 to sorafenib 400 mg twice daily and 303 to matching placebo.

Demographics and baseline disease characteristics were similar between the sorafenib and placebo arms. Prior treatments included surgical resections (20 percent), locoregional therapies (including radiofrequency ablation, percutaneous ethanol injection and transarterial chemoembolization in 40 percent), radiotherapy (5 percent), and systemic therapy (4 percent). Disease etiology was balanced in both sorafenib and placebo groups: HCV infection (29% vs 27%), alcohol-associated liver disease (26% both arms) and HBV infection (19% vs 18%).

The trial was stopped following a pre-specified second interim analysis for survival disclosing a statistically significant advantage for sorafenib [median 10.7 vs. 7.9 months; HR: 0.69 (95% CI: 0.55, 0.87), p= 0.00058]. The final analysis of time-to-tumor progression (TTP) by independent radiologic review was based on data from an earlier time point and demonstrated a statistically significant improvement in TTP in the sorafenib arm [median 5.5 vs. 2.8 months; HR: 0.58 (95% CI: 0.45, 0.74), p=0.000007]. In a subset analysis, patients with macrovascular invasion, the hazard ratio for OS favored sorafenib over placebo: HR 0.68 (95% CI 0.49 – 0.93).

To obtain regulatory approval in China a parallel study of sorafenib was undertaken in the Asia-Pacific region, where chronic hepatitis B virus infection is an important etiology factor. In 23 sites in China, Taiwan and Korea, Child Pugh A status patients were randomized in a 2:1 ratio to receive sorafenib (400 mg) or placebo twice daily in 6 week cycles. Of the 271 enrolled patients, 226 were randomized to receive placebo (N=76) or sorafenib (N=150). Demographic and baseline characteristics were similar in both arms as was hepatitis virus status: HBV infection was more common (70.7% sorafenib v.s 77.6% placebo) than HCV infection (10.7% sorafenib vs. 3.9% placebo).

Median overall survival was 6.5 months (95% CI 5.56 - 7.56) with sorafenib compared to 4.2 months (95% CI 3.75 - 5.46) with a hazard ratio of 0.68 (95% CI 0.5 - 0.93)[p=0.014]. Median TTP was 2.8 months (95% CI 2.63—3.58) in the sorafenib group compared with 1.4 months (95% CI 1.35—1.55) in the placebo group (HR 0.57 [95% CI 0.42—0.79]; p=0.0005). Adverse events and efficacy endpoint hazard ratios were consistent with those reported in the SHARP study, indicating similar action of sorafenib in both populations. Subsequent exploratory sub-set analyses in patients with macrovascular invasion and extra hepatic metastases, showed median OS of 5.6 months with sorafenib vs. 4.1 months with placebo; HR 0.75 (95% CI 0.54 - 1.05) and median TTP of 2.7 months with sorafenib vs. 1.3 months placebo; HR 0.58 (95% CI 0.41-0.83).

Sorafenib is now considered the standard of care therapy for patients with advanced HCC, the patients classified as BCLC C according to the Barcelona Clinic Liver Cancer (BCLC) classification system. These authors also suggest using sorafenib as the control arm for randomized clinical trials of first-line systemic agents. Sorafenib is included in the NCCN Clinical Practice Guidelines in Oncology9 (NCCN- Hepatobiliary cancers V.2.2012 - HCC6) and the EASL-EORTC Clinical Practice Guidelines as one of the possible treatments for patients with unresectable HCC and extensive liver disease who are not candidates for transplantation.

Although sorafenib is a standard of care in the treatment of patients with HCC, it is associated with only a modest improvement in median survival as compared to best supportive care. Further, sorafenib treatment is associated with significant toxicity. The most common adverse reactions (≥20 percent) considered related to sorafenib were fatigue, weight loss, rash/ desquamation, hand-foot skin reaction, alopecia, diarrhea, anorexia, nausea and abdominal pain. Diarrhea was reported in 55 percent of sorafenib patients (grade 3 in 10 percent). Hand-foot syndrome (21 percent overall; grade 3 in 8 percent) and rash (19 percent overall; grade 3 in 1 percent) were the most common dermatologic adverse reactions to sorafenib. Sorafenib dose reductions and drug holidays are often required to manage these toxicities.

Subsequent subset analysis of the SHARP trial data 10 indicated that the efficacy of Sorafenib is reduced in an important subset of patients with advanced HCC. In patients with extrahepatic spread or macroscopic vascular invasion, the median survival was 8.9 months in patients treated with sorafenib as compared to 6.7 months in patients treated with placebo.

Salem et al demonstrated the tolerability of TheraSphere in treatment of patients with HCC and branch PVT11 and patients with unresectable HCC12. Salem et al13 recently published their long-term experience of TheraSphere in the treatment of patients with HCC. In this report, patients with HCC (n=291) were treated with TheraSphere as part of a single-center, prospective, longitudinal cohort study. Toxicities were recorded using the Common Terminology Criteria version 3.0. Response rate and time to progression (TTP) were determined using World Health Organization (WHO) and European Association for the Study of the Liver (EASL) guidelines. Survival by stage was assessed. Univariate/multivariate analyses were performed. A total of 526 treatments were administered (mean, 1.8; range, 1-5). Toxicities included fatigue (57%), pain (23%), and nausea/vomiting (20%); 19% exhibited grade 3/4 bilirubin toxicity. The 30-day mortality rate was 3%. Response rates were 42% and 57% based on WHO and EASL criteria, respectively. The overall TTP was 7.9 months (95% confidence interval, 6-10.3). Survival times differed between patients with Child-Pugh A and B disease (A, 17.2 months; B, 7.7 months; P = .002). Patients with Child-Pugh B disease who had portal vein thrombosis (PVT) survived 5.6 months (95% confidence interval, 4.5-6.7). Baseline age; gender; performance status; presence of portal hypertension; tumor distribution; levels of bilirubin, albumin, and alphafetoprotein; and WHO/EASL response rate predicted survival. These investigators concluded that patients with Child-Pugh A disease, with or without PVT, benefited most from treatment. Patients with Child-Pugh B disease who had PVT had poor outcomes. TTP and overall survival varied by patient stage at baseline.

The clinical experience of Salem et al and a recent meta-analysis of yttrium-90 microsphere radioembolization indicates that TheraSphere is very well tolerated when appropriate patient selection criteria are used. Early reports 15 of serious adverse events possibly associated with the use of TheraSphere, as described in the package labeling documents in Appendix 1, included death, hepatorenal failure, liver abscess, hepatic encephalopathy, hepatic decompensation, radiation hepatitis, radiation pneumonitis, duodenal ulcer, gastrointestinal bleeding and cholecystitis. These more severe events are now uncommon as patients with the high risk factors associated with the occurrence of these events are typically excluded from treatment with TheraSphere. Patients in whom TheraSphere should be used with caution include those with infiltrative tumor type, bulk disease (tumor volume >70% or nodules too numerous to count), AST or ALT > five times the upper limit of normal, bilirubin > 2 mg/dL, tumor volume >50% in the presence of an albumin < 3 g/dL, and those in whom extra-hepatic shunting to the lungs or gastrointestinal tract cannot be managed through standard angiographic techniques.

Recent clinical data in patients with HCC and PVT indicate this group of patients may have a better outcome following TheraSphere treatment as compared to sorafenib treatment. Salem et al indicates that median survival in this group of patients following TheraSphere treatment ranges from 7.7 months (main PVT) to 16.6

months (branch PVT) with an overall average of 10.4 months. A recent paper by Mazzaferro et al reported a median overall survival of 13 months in a cohort of 35 patients with PVT treated with TheraSphere.

